4.2. RECRUITMENT

4.2.1. Recruitment Strategy

We do not anticipate contacting potential participants directly, and will not have access to medical records to identify women for inclusion. Potential enrollees may learn of the study from many sources, including: the NICHD Website, the PregSourceSM Website (or downloading the PregSourceSM app), our partner organizations¹, a participant’s doctor or midwife (via professional organizations), or by word of mouth from friends, family members, and other participants.

In addition, NICHD’s Public Communications Branch will draft posts about PregSourceSM for NICHD’s social media outlets (<https://www.facebook.com/nichdgov> and https://twitter.com/nichd_nih).

The Website will provide information that explains the purpose of data collection, what participation involves, risks and benefits, alternatives to participation, an explanation of how

¹ Partner organizations include: the American Academy of Pediatrics; the American College of Obstetricians and Gynecologists; the American College of Nurse-Midwives; American Society for Reproductive Medicine; Office of Research on Women’s Health; , Centers for Disease Control and Prevention; Health Resources and Services Administration ; Lamaze International, Preeclampsia Foundation; Obstetric and Neonatal Nurses; Office of Behavioral and Social Sciences Research ; the March of Dimes; and the Society for Maternal-Fetal Medicine and several NIH institutes such as NCCIH, NHLBI, NIEHS, NINR and NIMHD.

the data will be used, and contact information for any questions about the research or their rights as a research subject.

4.2.2. Recruiting Non-English Speakers

We will launch the main PregSourceSM website and app in English first. After that, the full website, main consent form, app, and questionnaires will be translated into additional languages, starting with Spanish.

We anticipate launching a fully translated Spanish version of PregSourceSM within 12 months of the launch of the English version. Creating a syntactically and culturally appropriate Spanish version means going beyond a straight word-for-word translation to also incorporate nuances in vocabulary, tone, idioms, and approach. The process is more akin to creating an entirely new website and application than to providing information in a different language because all PregSourceSM content will be affected: from questionnaires and consent documents to help information and system error messages to color schemes and images.

This effort will be led by the NICHD Office of Communications, which has successfully led several other similar projects including the creation of the Spanish version of DS-Connect[®]: The Down Syndrome Registry and the Spanish subsite of the main NICHD website. The plan outlined below is based on the team's experience with other similar projects.

1. After English website and app are launched, identify, program, and get IRB approval for additional modifications as needed. (15 weeks)
2. Outline translation requirements (i.e., setting freeze date for English content, identifying neutral Spanish words and phrases for use throughout, selecting a neutral Spanish editing style guide, listing staff roles and responsibilities, developing draft deliverable schedule, etc.). (2 weeks)
3. Freezes English version of website and/the app, inventory English content, and pulls into spreadsheet with appropriate technical information. (3 weeks)
4. Provides spreadsheet to American Translation Association-certified translator(s), who then translate the content. This activity comprises the bulk of the timeframe and includes some review and discussion with subject matter and other experts to ensure original intent of questions/content is maintained. (10 weeks)
5. Translator(s) return translated content to programmers, who then build the new website and application in a development or production environment. (7 weeks)
6. Once the site and/app are fully programmed, translators, technical experts, subject matter experts, security experts, and others review the content and function of the site and/app and make any necessary changes. Obtain IRB approval for revisions. (5 weeks)
7. Beta testing begins with different users focused on different aspects of the site/app: some are reviewing for content clarity, others for user experience, and others for overall function and security. All teams discuss suggested changes before they are incorporated. (4 weeks)
8. Final translated content is sent to the IRB for review and approval. (3 weeks)

9. Once approved, the site/app moves from development/production environment to live environment and technical and security experts verify technical and security functions. The English version content is unfrozen. (3 weeks)
10. Maintenance and minor revisions are ongoing as users work in and through the English and Spanish versions. Plans for any changes should include both English and Spanish versions. Analysis of functionality and use is also ongoing for both English and Spanish versions (currently using Google Analytics, but specific tools may change over time).

4.2.3. Recruitment Advertising

Recruitment and retention are critical to the success of a project like PregSourceSM, and we intend to employ multiple strategies and tactics at different times throughout the project to achieve our target goals. The tactics may vary from creating radio and transit ads, to providing materials and information for intermediaries (in this case, care providers), to working with and through online and in-person communities, to utilizing sponsored referrals. The specific tactics used will depend on many factors, such as the signup rates, the survey completion rates, participant demographic coverage, and the geographic areas in which we will focus our initial efforts.

The NICHD will rely on its many Partners to help engage their constituents and encourage women to participate. For example:

- The American College of Obstetricians and Gynecologists, the Society for Maternal-Fetal Medicine, and the Association of Women's Health, Obstetric, and Neonatal Nurses, have already agreed to recommend that their members promote PregSourceSM and will share NICHD-provided materials and information with their members to make this promotion easy and cost-effective.
- The Health Resources and Services Administration, the Centers for Disease Control and Prevention, and the March of Dimes have indicated that they will promote the website/app through their local chapters and regional maternal and child health offices and departments.

We plan to create an array of items for multiple channels and types of media that we will share with all of our partners and will make them publically available to non-partners. These will include (but are not limited to): social media messages and graphics, slides that can be inserted into presentations, flyers that are easily reproducible, text that can be dropped into a newsletter or conference program, digital badges that women can include in their social media profiles indicating that they are participating, posters for clinics and provider offices, emails that can easily be distributed over existing listservs and distribution lists, designs for displays that can be used at health fairs or in birthing classes, posting information about the site/app in online resources such as clinicaltrials.gov and ResearchMatch, etc.

NICHD will also issue press releases via the NICHD and/or NIH Communications Offices. NICHD's Website will also post a description of the research registry, along with a link to the main website, and include information in appropriate lists of similar registries and trials, such as the

NIH List of Registries webpage (<http://www.nih.gov/health/clinicaltrials/registries.htm>). Similar registry descriptions may be available in electronic and/or printed handouts.

In addition, according to the Pew Research Center, when Americans look for health information online, three-quarters of them begin by using a search engine (Fox 2013). If recruitment is slow, Google AdWords and other online mechanisms may be used to boost the online profile of PregSourceSM in such searches.

Concurrent to the culturally appropriate translation process, the NICHD will develop a promotion plan for the Spanish version of the site and app. The promotion plan will involve PregSourceSM partners and other organizations, such as the National Hispanic Medical Association (NHMA) and the National Hispanic Nurses Association (NHNA), as well as community groups, such as the Mary's Centers for Maternal and Child Care, and other agencies, such as the HHS Office of Minority Health. Specific tactics for promoting the Spanish website's availability include (but are not limited to): contributing information and visuals for NHMA, NHNA, and others to include in their newsletters, electronic updates, and other communications with their constituents for providers to share with their patients; creating online assets that NICHD and PregSourceSM partners can incorporate into their websites and social media accounts; sending out announcements and notices using outlets such as Hispanic PR Newswire; conducting some face-to-face outreach at Mary's Centers and other community venues; and asking Gobiernousa.gov (the official web portal of the United States Government in Spanish) and other resource sites to include information about PregSourceSM on their sites. The messages and materials will be ready to share when the Spanish site/app are launched.

If during data monitoring (see Section 7.2.4, Monitoring Recruitment and Sample Population), PregSourceSM identifies under-represented groups, we will develop and implement similar targeted recruitment and outreach efforts to enroll participants in these groups.

4.2.4. Anticipated Accrual Rate

There is no limit on the number of participants in PregSourceSM. At this time it is difficult to estimate accurately how many women may choose to register, how many will enter – and continue to enter – data throughout their pregnancy, and what the accrual rate is likely to be. The immediate goal is to accrue 10,000 participants within 2 years of launch.

4.2.5. Recruitment Replacement Strategy

If a participant decides to withdraw her information from the database, no specific effort will be made to replace that individual.

4.3. SCREENING

A potential participant will self-register online via the Website or app without providing proof of eligibility (e.g., a medical diagnosis). The Website will provide general information about the registry on a Frequently Asked Questions webpage.

Participants must complete the online consent form before they can enter data.

4.4. STUDY PROCEDURES

4.4.1. Consent Documents and Process

Who obtains consent. Informed consent will be collected electronically via the Internet; study staff will not obtain verbal or in-person informed consent. Each subject will read, complete, and submit an online consent form herself.

Consent procedure. To join the study, a participant will need to:

1. Create an account by going online to the PregSourceSM Website, <https://PregSource.nih.gov>. The Website can be accessed via computer or the app. Apps will be available for downloading in both iPhone and Android versions. The participant will need to choose a unique user name and a password.
2. Review and complete the online consent form.

Consent documents. A Frequently Asked Questions (FAQs) document will be available on the Website to help address questions participants may have, such as: what is the purpose of the study, what does participation involve, what are the known risks and benefits of participation, how will the data be used, and contact information for further questions. A copy of the electronically signed consent responses will be saved in each participant's Profile for future reference. The PregSourceSM Privacy Policy and Terms and Conditions will also be available on the Website. In addition, Coordinators will be available via email (posted on the "Contact Us" webpage) during regular business hours to answer questions.

Consent to re-contact for follow-up. After completing the consent and registration process, a participant will be asked, as part of completing her account profile, whether she is willing to be contacted by PregSourceSM staff about studies and clinical trials she may be eligible to participate in. The original consent will be part of her account profile, and she will be able to change her Contact and Sharing Preferences at any time.

4.4.2. Account Profile Set up and Health History Questionnaire

Once registered and consented, a participant can begin to enter information after reading the PregSourceSM Privacy Policy and Terms and Conditions of use, then completing her Account Profile and taking an initial Health History questionnaire to collect data on:

- Contact information and preferences (email, text, etc.), including an optional alternate contact²
- Demographics and socioeconomic -- NIH-required race/ethnicity data, general family income ranges, education levels

² Alternate Contacts will be contacted only in cases when repeated attempts to gather final pregnancy outcome information have been unsuccessful.

- Interest in participating in a clinical trial. The participant will be asked for her consent to allow the PregSourceSM coordinators to contact her regarding future opportunities for participation in a clinical trial or research study.
- Pre-pregnancy general health – height, weight, a checklist for chronic conditions (e.g., diabetes, lupus), medications
- Reproductive health – contraceptive use, previous pregnancy histories, infertility, use of assisted reproductive technologies
- Current pregnancy health – gestational age, number of fetuses, date of first prenatal visit, prenatal visits completed, any diagnoses received or test results.

A participant will access PregSourceSM questionnaires online and/or via a mobile app to enter her own data. She will be able to download apps (e.g., via the iTunes or Android online app stores) to a smartphone or tablet, and connect these to her online account.³ The apps, as well as the Website, will let her access and enter data into online surveys and trackers. A participant will also be sent reminders and push notifications, asking her to update her information.

All questionnaires will be constructed using “Smart Survey Design” – i.e., using conditional or skip logic to add or skip questions that are not relevant, based on previous answers. Aggregated data will help us analyze response frequencies for survey questions.

4.4.2.1. Trackers

Each participant can enter data in a set of health “trackers” – online or in-app software diaries that capture daily or weekly information over the course of pregnancy about her weight, nausea symptoms, mood, and sleep. Additional trackers may be added at a later date for tracking nutrition, exercise, and pain. She can enter data in the trackers as often as she chooses. We anticipate that for trackers such as nausea, sleep, and mood, a participant might enter data on a daily basis; while weight data might be entered only once a week or even once a month. Most trackers will collect data on timing, duration, severity/intensity, and related issues. A 2013 report by Citrix⁴, a software company that tracks app usage, shows pregnancy related apps to have wider usage. Many of the available trackers have been used and/or validated in the pregnant population⁵. Recent research articles⁶ have demonstrated the use of web-based methods to collect relevant health related information from pregnant women.

Unless otherwise indicated in her Account Profile, a participant will be reminded on a weekly basis to update her information, if she has not entered new data within the past two weeks.

³ Participants will not be required to use the apps. The apps will be available as a potentially more readily available means of accessing the questionnaires and trackers.

⁴ Nick Bilton, New York Times, August 26, 2015

⁵ Hämeen-Anttila K, Nordeng H, Kokki E, Jyrkkä J, Lupattelli A, Vainio K, Enlund H. Multiple information sources and consequences of conflicting information about medicine use during pregnancy: a multinational Internet-based survey. *J Med Internet Res.* 2014 Feb 20;16(2).

⁶ Wise LA, Mikkelsen EM, Rothman KJ, Riis AH, Sørensen HT, Huybrechts KF, Hatch EE. A prospective cohort study of menstrual characteristics and time to pregnancy. *Am J Epidemiol.* 2011 Sep 15;174(6):701-9

We anticipate including the following trackers:

Weight tracker. Weight would likely be entered weekly/monthly. Data collected includes:

- Weight (in pounds or kilograms)⁷

Nausea tracker. The Nausea Tracker could be entered as often as necessary, collecting data on:

- Date
- Timing (morning, afternoon, all day)
- Duration
- Severity (just nauseous, vomited)

Sleep tracker. In addition to asking about a participant's sleep patterns and apnea diagnosis prior to pregnancy in the initial health questionnaire, the Sleep Tracker may collect data on:

- Number of hours of sleep each night
- Quality of sleep (slept soundly, tossed and turned, etc.)
- Sleep position (back, stomach, right side, left side)

Activity tracker. Activity could be entered as often as necessary. It may collect data on:

- Intensity of physical activity
- Duration of physical activity

Mood tracker. The Mood Tracker could be entered as often as necessary. We will use the validated Positive and Negative Affect Schedule (PANAS) (Watson D and Clark LA 1994; Thompson ER 2007). This measure has also been used to access psychological stress among women with and without reproductive failure (Coughlan C et al 2014). It may collect:

- Mood description

As per Section 7.1.1.1 Safety: "If a participant enters data indicating a health or safety concern, the database will send an automated notice to her that she may want to contact her doctor for advice. The database may also refer her to related factsheets and websites with further information." In PregSourceSM, after a participant enters data for the PANAS, the platform will calculate raw scores for both positive affect (PA) and negative affect (NA). Crawford (2010) reported norms for the PA and NA scores on the PANAS instrument. Because the data were not normally distributed, they converted the data into percentiles. The Crawford nomogram will be used to convert raw scores into percentiles. Participants who score >95th percentile for NA and/or <5th percentile for PA will be considered to have affect that deserves further attention by a clinician. Participants with scores in these ranges will receive a notification stating that their mood may indicate a problem that they may want to discuss with their care provider. Participants will also receive a follow-up message 2 weeks after the initial notification

⁷ Height data would be collected in the Initial Health Questionnaire, so that BMI can be calculated. We would ask in the Gestational Age monthly questionnaires if there was any change in height (not likely for adults, but may change for teenagers).

reminding them that their mood tracker indicated a concern that may warrant discussion with their health care provider.

Medications in pregnancy tracker. The Medications Tracker may ask if the women have:

- Taken any medications for specific conditions
- When they stopped taking the medication
- Reason for the medication being used

Alternative therapies tracker. The Alternative Therapies Tracker may ask women if they are taking any alternative medications or herbal supplements, reasons for their use, and how many are taken without clinician recommendation:

- Any herbal supplements or alternative medications used?
- If yes, which therapies?
- Reason for use

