2.2. SECONDARY OBJECTIVES

To measure the impact that pregnancy symptoms and treatments have on women's lives.

Examples of the overarching questions and measures include:

- Nausea and vomiting during pregnancy – to identify how often this affects pregnancy, its timing, treatments, and impact on weight
 - How often and at what gestational age do nausea and vomiting begin/improve?
 - Impact on weight
 - Treatments
- Physical disabilities and pregnancy – to identify how many pregnancies may be affected by physical disabilities
 - What disability?
 - Impact on pregnancy
 - Impact of pregnancy on the condition
- Weight gain in pregnancy – to identify weight gain patterns in pregnancy and compare to Institute of Medicine guidelines
 - Pre-pregnancy weight and height
 - Weight weekly or monthly
 - Plot weight gain on the appropriate IOM guideline chart
- Activity/Exercise in pregnancy – to identify exercise patterns in pregnancy including type and amount of exercise, impact on pregnancy
 - Evaluation of moderate and high impact activities across pregnancy
- Sleep in pregnancy – to identify sleep patterns in pregnancy including number of hours, sleep quality, and sleep position
 - Sleep pattern prior to pregnancy
 - Number of hours (on average) sleep per night
 - Quality of sleep
 - Prevalence of sleep apnea
 - Sleep position
- Mood in Pregnancy – to identify general mood in pregnant women throughout gestation. This will be done via a Mood Tracker and mood may be entered as often as necessary. We will use the validated Positive and Negative Affect Schedule (PANAS)

(Watson D and Clark LA 1994; Thompson ER 2007). This measure has also been used to access psychological stress among women with and without reproductive failure (Coughlan C et al 2014). It may collect mood descriptions such as excited, irritable, angry, jittery, etc.

- Medications in pregnancy – to identify how many medications women are taking, reasons for their use, and how many are taken without clinician recommendation
 - Any medications used (weekly query) with triggers of those input in prior week to allow a continuation or stopping of that medication
 - Reason for the medication being used
 - Did a medical provider recommend the medication or is it being used over the counter?

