2.3.2. Secondary Outcome Measures

- Proportion of pregnant women who experience nausea and vomiting in pregnancy across gestation
- Proportion of pregnancies that are impacted by physical disabilities
- Weight gain patterns in pregnancy with a comparison to IOM guidelines
- Exercise patterns in pregnancy including type and amount of exercise, impact on pregnancy
- Sleep patterns in pregnancy including number of hours, sleep quality, and sleep position
- How many medications women are taking, reasons for their use, and how many are taken without clinician recommendation
- How many alternative medications /herbal supplements pregnant women are taking, reasons for their use, and how many are taken without clinician recommendation
- Number of ultrasounds in pregnancy

In the future, additional measures may be added, such as assessments of maternal mental health, stress, chronic conditions such as hypertension and diabetes, and assessment of maternal diet and other environmental factors.

SECTION 3. STUDY POPULATION

This will be a prospective cohort study, collecting information from women of child-bearing age who are pregnant. The study will include healthy volunteers, as well as those with pre-conception medical conditions and/or pregnancy complications. Because it will be online, there is no limit to the number of participants who can join. It will be focused on women in the United States, but because it will be online, women in other countries may also participate.

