4.4.2.2. Gestational Age Questionnaires

Once a month, PregSourceSM will send each participant an email, text, or app push notification, with a link to a new questionnaire relevant to her current week of gestation. For example, at 25 weeks of gestation, we may ask whether she has felt her baby move yet. At the end of each questionnaire, if the participant has not entered data into the health trackers in the past month, she will be taken to the appropriate trackers to enter information. This process will allow PregSourceSM to reduce duplication of questions, and capture changes over time in a consistent manner (e.g., all weight data will be entered into the Weight tracker).

If a participant does not complete her monthly questionnaire, she will receive a reminder once a week to do so via email or text to review the information she has entered into the database and provide any appropriate updates to her information.

Gestational-age questionnaires will continue monthly through pregnancy and then quarterly up to 36-months post-partum to capture information on maternal recovery and neonatal and infant outcomes and development.

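### As listed, the voluntary Nausea Tracker can record only symptoms, so the nausea proportion per gestational period is bounded only from below and the time of resolution cannot be dated.

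*Protocol*

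**What the plan says.** Protocol Section 4.4.2.1 gives the Nausea Tracker four fields: date, timing, duration and severity. Timing is listed as "Timing (morning, afternoon, all day" and severity as "Severity (just nauseous, vomited". On frequency, the section says: "She can enter data in the trackers as often as she chooses".

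Two prompts are described:
- A weekly reminder (Section 4.4.2.1), sent "if she has not entered new data within the past two weeks". It is worded for new data in general, not for each tracker.
- A redirect at the end of each monthly questionnaire (Section 4.4.2.2): "if the participant has not entered data into the health trackers in the past month, she will be taken to the appropriate trackers". The stated purpose is to avoid asking the same thing twice and to capture change consistently.

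Section 2.3.2 lists as its first secondary outcome: "Proportion of pregnant women who experience nausea and vomiting in pregnancy across gestation". The first example question in Section 2.2 is: "How often and at what gestational age do nausea and vomiting begin/improve".

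**The concern.** A proportion needs women known to be symptom-free as well as women known to have symptoms. Every value listed for the Nausea Tracker describes an episode, so a woman who feels well has nothing to enter. If she keeps logging weight or sleep, she remains active, yet her empty nausea record could mean either that she had no nausea or that she did not log it.

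The topic is central to the registry. Section 1 opens its list of unanswered questions with how common morning sickness is, how long it lasts and when it occurs. Section 1 and Section 6.4.2 also promise participants a comparison with other women on this symptom. This is a matter of data capture: if symptom-free time is never recorded, no later analysis can supply it.

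**Working it through.** The protocol states no figure on this point, so there is none to reproduce. The check has two parts.

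**1. Can any described route record a symptom-free state?**
- *Tracker fields.* No listed value means none.
- *Weekly reminder.* Read as written, a weight entry within two weeks is enough to switch it off.
- *Monthly redirect.* It can be read as applying to each empty tracker, or only when no tracker was used. On either reading it leads to the same symptomatic fields.
- *Health History (Section 4.4.2) and monthly questionnaire (Section 4.4.2.2).* No nausea item is described in either.
- *Dropout (Section 7.2.3).* It requires more than 3 months without data, so it does not flag a nausea gap in a woman who is active elsewhere.

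By contrast, the Alternative Therapies Tracker in Section 4.4.2.1 first asks about any use and then continues "If yes, which therapies", so a negative can be recorded there.

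**2. What can the data then show?** All inputs here are assumed. Among active women in one month, let p be the true proportion with nausea, s the share of affected women who log it, and r the response of symptom-free women relative to s. Logging by affected women is held the same with and without the added level.

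- As listed: logged share = p × s. Everyone else could be affected, so the compatible range is [p × s, 1].
- With a no-symptom level: share answering none = (1 − p) × s × r, so the range is [p × s, 1 − (1 − p) × s × r].

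With p = 0.5 (width in points in brackets):

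| s | As listed | Added level, r = 1 | r = 0.75 | r = 0.5 |
|---|---|---|---|---|
| 0.8 | 40-100% (60) | 40-60% (20) | 40-70% (30) | 40-80% (40) |
| 0.4 | 20-100% (80) | 20-80% (60) | 20-85% (65) | 20-90% (70) |

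For example, at s = 0.8 and r = 0.75 the share answering none is 0.5 × 0.8 × 0.75 = 0.30, so the upper limit is 1 − 0.30 = 0.70. In every cell the width falls by exactly the share answering none.

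*Point estimates.* As listed, reading silence as no nausea gives 40% (s = 0.8) or 20% (s = 0.4), and the figure among women with an entry is always 100%. With the added level, the estimate among responders is 0.5 / (0.5 + 0.5r) = 50%, 57% or 67% for r = 1, 0.75 or 0.5. The 67% is 17 points from the truth, against 10 points for the 40%.

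*Change over gestation.* Suppose true prevalence stays at 60% while logging falls from 80% to 40%. The logged share goes from 0.6 × 0.8 = 48% to 0.6 × 0.4 = 24%, an apparent improvement produced by logging alone.

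*Timing.* The first entry shows that onset was no later than that date. A move from vomiting to nausea only shows partial improvement. The last entry shows that symptoms had not ended before it, but nothing listed shows when they did end.

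**The case against.** The strongest reply is that this reads an outline as a finished form. The trackers are introduced as what the registry expects to include. The bracketed timing values omit evening and night, so they may not be the full response set, and whether duration accepts zero is not stated. Section 4.4.2 says all questionnaires use skip logic, which is compatible with a gate question. The contrast with the Alternative Therapies Tracker may be drafting style: the Activity Tracker also lists only intensity and duration. Outcomes are descriptive, Section 8.1 plans no statistical analysis in advance, and Sections 4.4.6, 4.4.2.4 and 7.2.3 provide for beta testing, revision and usage monitoring.

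Much of this stands. A reader might infer that the registry will have no nausea denominator at all. The documents do not support that, because the screens and questionnaire texts are not shown. The point is therefore conditional on the fields as listed.

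It does not remove the point. These bullets are the only nausea specification in the protocol, and the aim of avoiding duplicate questions means a monthly nausea item cannot be presumed. Usage monitoring cannot settle it either, since few nausea entries could reflect wellness or disengagement. The provision for revision is a reason to settle the point before launch, because periods already passed cannot be recovered.

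**Conclusion.** The point holds for the tracker as listed and is worth fixing before launch. For women active elsewhere, symptom-free time and missed logging are indistinguishable. The proportion per gestational period therefore has the logged share as its lower bound and no informative upper bound, and resolution cannot be dated.

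It would go too far to say that nausea prevalence and improvement are wholly unidentifiable. Entries still give a lower bound on the proportion, a latest date for onset, and evidence of partial improvement.

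The widths shown (60 or 80 points as listed) rest on an assumed 50% prevalence and 40-80% logging. They illustrate the mechanism and do not estimate its size in this registry.

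**What to change.** - **Section 4.4.2.1:** add a level for no nausea or vomiting to the Nausea Tracker, with a stated reference period, for example since the last entry.
- **Section 4.4.2.2:** state that each monthly questionnaire takes every participant to this item, whether or not she logged nausea earlier that month or used another tracker. Prompting only women with an empty month would leave silence after an early-month entry ambiguous. The rule also settles, for nausea, which trackers the redirect covers.

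Symptom-free time since the last entry is then recorded separately from non-response, and the bounds narrow by the share who answer none. The change does not guarantee a less biased estimate, because symptom-free women may respond less often; that should be stated wherever the figure is reported.

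The cost is one response level, one prompt rule, IRB review of the wording, and a few seconds per participant per month. If the built tracker or the monthly questionnaire already has such an item, stating so in the protocol is enough, provided that it has a reference period and is put to every participant.
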